5.3 Eligibility Criteria

5.3.1 General Eligibility Criteria

Assessment for general eligibility criteria is based on medical records of the site and interview with a candidate patient. Patients must meet ALL general inclusion criteria to participate in the clinical investigation. If ANY general exclusion criteria are met, the patient is excluded from the clinical investigation and cannot be enrolled.

If any clinical and/or laboratory tests are required for patient screening and are not included in a site's standard tests, they must be completed after written informed consent is obtained.

Clinical Investigation Plan for Europe

5.3.2 Inclusion Criteria

5.3.2.1 General Inclusion Criteria

1. Subject must have at least one of the clinical indications before device implant in adherence with ACC/AHA/HRS/ESC dual chamber pacing guidelines
2. Subject is ≥ 18 years of age or age of legal consent, whichever age is greater
3. Subject has a life expectancy of at least one year
4. Subject is willing to comply with clinical investigation procedures and agrees to return to clinic for all required follow-up visits, tests, and exams
5. Subject has been informed of the nature of the clinical investigation, agrees to its provisions and has provided a signed written informed consent, approved by the IRB/EC

5.3.3 Exclusion Criteria

5.3.3.1 General Exclusion Criteria

1. Subject is currently participating in another clinical investigation that may confound the results of this study as determined by the Sponsor
2. Subject is pregnant or nursing and those who plan pregnancy during the clinical investigation follow-up period
3. Subject has presence of anatomic or comorbid conditions, or other medical, social, or psychological conditions that, in the investigator's opinion, could confound the assessment of the investigational device and/or implant procedure, limit the subject's ability to participate in the clinical investigation or to comply with follow-up requirements of the clinical investigation results
4. Subject has a known allergy or hypersensitivity to < 1 mg of dexamethasone sodium phosphate or any blood or tissue contacting material listed in the IFU
5. Subject has an implanted vena cava filter or mechanical tricuspid valve prosthesis
6. Subject has pre-existing, permanent endocardial pacing or defibrillation leads (does not include lead fragments)
7. Subject has current implantation of either conventional or subcutaneous implantable cardioverter defibrillator (ICD) or cardiac resynchronization therapy (CRT) device
8. Subject has an implanted leadless cardiac pacemaker (except for an Aveir ventricular LP)
9. Subject is implanted with an electrically-active implantable medical device with stimulation capabilities (such as neurological or cardiac stimulators)*
10. Subject is unable to read or write

*NOTE: Does not apply to a medical device with no known impact to the Aveir Leadless Pacemaker System, including the Aveir Link Module. Patient evaluation and the decision to implant the LP should take into account the presence of other active implantable devices and should include consultation with the Sponsor and/or manufacturer of the co-existing device.

Clinical Investigation Plan for Europe

5.4 Subject Enrollment

A patient is considered enrolled in the clinical investigation from the moment the patient provides written informed consent.

All enrolled subjects who meet eligibility criteria should undergo an attempted implant. A subject may withdraw or be withdrawn prior to the implant attempt. If an enrolled subject does not undergo an attempted implant, the subject should be withdrawn as soon as possible.

If subjects receive a device without meeting all the conditions listed above, they should still complete all follow-up requirements. These subjects are considered CIP deviations.

5.4.1 Historically Under-Represented Demographic Subgroups

The Sponsor intends to implement FDA's guidance on sex-specific data in medical device clinical investigations to ensure adequate representation of women and other traditionally under-represented demographic subgroups in this clinical investigation. As noted in the guidance, some barriers to participation of women and ethnic minorities in clinical investigations have traditionally been:

- Lack of understanding about main obstacles to participation of such subgroups in clinical research
- Inclusion/exclusion criteria potentially not needed to define the clinical investigation population may unintentionally exclude specific subgroups
- Under diagnosis of disease etiologies and pathophysiology leading to under referral of demographic subgroups
- Avoidance of specific subgroups by investigators and Sponsors due to the perception that it takes more time and resources to recruit them
- Fear of fetal consequences (for female participants)
- Family responsibilities limiting women's ability to commit time for follow-up requirements

Historically, Phase 1 of the Leadless II IDE trial, mainly in the US, included 38% females, an average age of 75.8 years, and 9% non-white ethnic minorities¹. This clinical investigation will also enroll subjects in the US and has identical criteria on the enrollment of female and minority ethnicity. As such, Abbott expects similar proportions of female and minority ethnicity for this study. The traditional barriers for female enrollment (such as fear or fetal consequence, family plan of new pregnancies that may limit the ability of time commitment to follow-up) are not applicable to this clinical investigation due to the expected average age of the patient population. Therefore, the eligibility criteria of this clinical study do not introduce gender or racial bias

¹ Vivek Y. Reddy, et al. Percutaneous Implantation of an Entirely Intracardiac Leadless Pacemaker. NEJM. 2015; 373:1125-1135.

Clinical Investigation Plan for Europe

The Sponsor will take the following steps to ensure adequate representation of women and racial or ethnic minorities in this clinical investigation:

1. The Sponsor will provide training to investigational site personnel to ensure adequate representation of these demographic subgroups
2. The Sponsor will regularly review enrollment data to investigate whether there is under-representation of these demographic subgroups
3. The Sponsor will regularly review withdrawal rates for under-represented subgroups and compare these rates with that in the overall clinical investigation population
4. As appropriate and necessary, the Sponsor will retrain sites on the importance of recruiting and retaining subjects in the clinical investigation
5. The Sponsor will approach sites without bias or consideration for specific demographic subgroups
6. The Sponsor will have informed consent materials in alternative languages and will work with sites and IRBs/ECs on recruitment materials

5.5 Subject Withdrawal and Discontinuation

Each subject meeting all general and screening eligibility criteria shall remain in the clinical investigation until completion of the required follow-up period; however, a subject's participation in any clinical investigation is voluntary and the subject has the right to withdraw at any time without penalty or loss of benefit. Conceivable reasons for discontinuation may include, but are not limited to, the following:

- Subject death
- Subject voluntary withdrawal
- Subject lost-to-follow-up
- Subject's follow-up is terminated according to Section 3.3
- Unsuccessful Implant
- LP explanted and not re-implanted
- LP abandoned and Aveir LP not re-implanted

Sites must notify the Sponsor of the reason(s) for subject discontinuation. Investigators must also report this to their respective IRB/EC as defined by their institution's procedure(s).

No additional follow-up is required or data recorded from subjects once withdrawn from the clinical investigation, except for the status (deceased/alive).

However, if a subject withdraws from the investigation due to problems related to the safety or performance of the device under investigation, the investigator shall ask for the subject's permission to follow his/her status/condition outside of the clinical investigation according to standard of care.

Lost-to-Follow-up

Clinical Investigation Plan for Europe

If the subject misses two consecutive scheduled follow-up time points and the attempts at contacting the subject detailed below are unsuccessful, then the subject is considered lost-to-follow-up. Site personnel shall make all reasonable efforts to locate and communicate with the subject (and document these efforts in the source documents), including the following, at each contact time point:

- A minimum of two telephone calls on different days over the specified follow-up windows to contact the subject should be recorded in the source documentation, including date, time and initials of site personnel trying to make contact.
- If these attempts are unsuccessful, the site should send a certified letter to the subject.
- If a subject misses one or more non-consecutive follow-up contact time points, it will be considered a missed visit. The subject may then return for subsequent visits. If the subject misses two consecutive time points and the above-mentioned attempts at communicating with the subject are unsuccessful, the subject will be considered lost-to-follow-up.

Note: Telephone contact with a General Practitioner, non-clinical investigation cardiologist or relative without the presence of the subject or indirect documentation obtained via discharge letters will not be considered as subject contact.

5.6 Number of Subjects

The clinical investigation will enroll up to 550 subjects at up to 85 sites worldwide to analyze the primary endpoints that is based on the following:

- 300 *de novo* subjects to evaluate the primary endpoints, including attrition
- Up to 200 *de novo* subjects [REDACTED]
- Up to 50 subjects to assess the upgradeability to a Aveir DR LP system in subjects previously implanted with the Aveir VR LP single chamber system

[REDACTED]

Subjects previously implanted with an Aveir VR LP who are enrolled to assess the upgradeability to an Aveir DR LP system (up to 50) will be concurrently enrolled with the *de novo* subjects but will not contribute toward the evaluation of the primary and secondary endpoints.

No site may enroll more than 15% of the total subjects required to evaluate the primary endpoints.

Clinical Investigation Plan for Europe

5.7 Total Expected Duration of the Clinical Investigation

The expected duration of each subject's participation in the clinical study is 1 year including the scheduled visits and data collection as listed in Section 6.6. All enrolled subjects will be followed through subject withdrawal or site closure, whichever occurs first. Site closure will not begin until all active subjects across all active study sites have completed their 12-month follow up visits or the 12-month visit window has passed and approval for commercial use is received from local regulatory agencies. For more information about the clinical investigation conclusion and site closure, see Section 13.0.

6.0 TREATMENT AND EVALUATION OF ENDPOINTS

6.1 Baseline Assessment

Investigators will document each subject's demographics including age at consent, sex, height, weight, and race/ethnicity (if applicable). Investigators will also document each subject's baseline medical history, including cardiopulmonary history, patient LP status (e.g. *de novo* or pre-existing Aveir LP), and cardiac medications. Investigators will document the cardiac drug categories for the cardiac medications (e.g. beta blockers, ACE inhibitors, ARBs, anti-coagulants, anti-platelets, anti-arrhythmics) as well as any changes to these medications during the follow-up period.

Investigators will obtain a 12-lead ECG only if one has not already been recorded within the last 30 days prior to the implant date. Investigators will administer an EQ-5D 5L quality of life survey to each subject prior to implant and record the responses. All subjects will undergo routine laboratory assessment per the site's standard of care.

For female subjects of childbearing age, investigators will document a pregnancy assessment according to the site's standard test method, which may include obtaining a blood sample for conducting a pregnancy test. Any pregnancy test must be done after the subject signs an ICF. A negative pregnancy test result must be obtained within 7 days prior to the index procedure.

6.1.1 Data Submission

Once the site has collected the required information and completed the required testing, the site will complete and submit the following case report forms to Abbott Medical using the EDC system:

- Enrollment Form
- Medical History Forms
- Quality of Life Assessment (EQ-5D 5L)
- Adverse Event Form, if applicable

Clinical Investigation Plan for Europe

- Deviation Form, if applicable
- COVID-19 Assessment Log, if applicable
- Study Withdrawal Form, if applicable

6.2 Implant Procedure

Please refer to the IFU for instructions on handling and preparation of the Aveir DR LP system. All Investigators must read and understand the IFU and Investigator Brochure (IB), as applicable. Sponsor representatives may also assist the team in equipment setup prior to and during a procedure.

6.2.1 Medications

Investigators will administer all medications per hospital standard of care for pacemaker implant and femoral venous catheterization procedures. Use of anticoagulation medications is not required with the implantation of the Aveir LP and is left to the investigator's discretion. During the procedure, appropriate anticoagulant therapy should be considered to reduce potential thrombus formation. Investigators will record any cardiac medications given prior to and during the implant procedure including beta blockers, ACE inhibitors, ARB, anti-coagulants, anti-platelets, and anti-arrhythmics.

6.2.2 Imaging

At a minimum, proper equipment must be available for high resolution fluoroscopy to assist with delivery and implantation of the LPs. The fluoroscopy must have the ability to record and save images, to zoom, and to obtain images in multiple projections, in accordance with the manufacturer's IFU.

Optional Imaging to Characterize Right Atrium

Investigators are also encouraged to use any other appropriate imaging modalities available at their sites during the procedure that can help characterize the right atrium/appendage and evaluate how the atrial LP is positioned relative to the local anatomy. Imaging modalities may include intraprocedural intracardiac echocardiography (ICE). Use of any supplemental imaging modalities is optional and is left to the investigator's discretion.

In addition, any pre-existing imaging of a subject's right atrium/appendage, such as pre-procedural MRI or CT, should be submitted to the Sponsor.

All imaging data obtained for the purpose of right atrial characterization should be de-identified and submitted to the Sponsor.

6.2.3 Femoral Vein Assessment and Access

The Sponsor supports using either ultrasound or fluoroscopic guidance techniques for assessing femoral vein access-site location, including evaluation of the size and presence of any disease. However, investigators will use medical judgment and follow institutional standards of care when

Clinical Investigation Plan for Europe

accessing the femoral vein for catheter-based procedures. Only approved investigators will perform femoral vein access.

Investigators will insert and remove any investigational introducer sheaths in accordance with the manufacturer's IFU.

6.2.4 LP Preparation and Implant

Investigators will prepare and implant the Aveir LPs in accordance with the manufacturer's IFU. Consult the IFU for implantation guidelines and general handling information. Only approved investigators will perform the implant procedure, including placement of the Aveir device.

If both atrial and ventricular LPs are implanted, pairing in dual-chamber mode and establishing i2i communication must be attempted at the end of the procedure to verify that the system can be programmed in a dual-chamber pacing mode. If verified, subjects should be discharged and remain in a dual-chamber pacing mode throughout the study period. Investigators are permitted to change the pacing mode at any time if clinically appropriate.

Following the placement of both LP devices, investigators should obtain a cinefluoroscopy for at least 2 cardiac cycles in orthogonal views to evaluate final LP placement.

6.2.5 LP Assessment and Programming

Investigators and/or Sponsor representatives will interrogate the Aveir DR LP system using the market-approved St. Jude Medical™ Merlin™ Patient Care System (Model 3330) with the Aveir Link Module (Model LSL02).

Sponsor representatives may assist investigators in assessing pacemaker effectiveness (for example pacing, sensing, and rate response effectiveness), downloading diagnostic information, and programming pacemaker parameters.

Investigators will measure and record the following parameters:

- Atrial and Ventricular LP Capture threshold at 0.4 ms pulse duration*
- Atrial and Ventricular LP Impedance
- Atrial and Ventricular LP Sense Amplitude*
- Atrial and Ventricular i2i throughput
- Atrial and Ventricular i2i setting level
- Battery Voltage**
- Device Longevity and Remaining Capacity to recommended replacement time (RRT)**

** Atrial and Ventricular sense amplitude measurements are not required if the subject's intrinsic rate has been established to be below 30 beats per minute. Atrial capture threshold and sense amplitudes are not required if the subject is in atrial fibrillation or atrial flutter. Ventricular capture thresholds are not required if a high ventricular rate is present.*

***Not required at implant or pre-discharge visits.*

Clinical Investigation Plan for Europe

To avoid potential complications associated with undersensing, Investigators shall program a sensing margin of at least two times the intrinsic cardiac amplitude (e.g. for an intrinsic R-wave of 4 mV, program the R-sensitivity ≤ 2 mV).

6.2.6 LP Repositioning and/or Release

Once the investigator implants an Aveir LP and successfully demonstrates acute effectiveness, the investigator may release the Aveir LP. When the investigator has released the Aveir LP, s/he will use fluoroscopy to assess positioning of the implanted LP.

Investigators may reposition the Aveir LP, if determined necessary. For release and repositioning procedures, refer to the IFU.

Once the Aveir LP has been released, investigators will use an Aveir Retrieval Catheter for removal, if needed (Refer to the Aveir Retrieval Catheter IFU). Once the LP has been removed, investigators may attempt to implant another Aveir LP, or instead, choose to implant a different market-approved pacemaker.

6.2.7 Subjects with two (2) LPs implanted

Investigators will follow subjects who leave an attempted *de novo* implant procedure with two Aveir LPs implanted through a minimum of 12-months post-implant according to the clinical investigation flowchart described in Figure 6.

6.2.8 Subjects with one (1) LP implanted

De Novo Subjects

Investigators will follow subjects who leave an attempted *de novo* implant procedure with one Aveir LP implanted through a minimum of 12-months post-implant according to the clinical investigation flowchart described in Figure 6.

The investigator must document the nature of and reasons for the unsuccessful LP implant on the Implant Form. Subjects who leave an index procedure with one LP implanted will not be eligible for re-implantation attempts of a second LP in a different chamber at a later date during the study period.

Upgrade Subjects

Investigators will follow subjects who leave an attempted *upgrade* procedure with an unsuccessfully implanted atrial LP for a period of at least 30 days to evaluate for adverse events. At the end of the 30 days, the investigator will withdraw the subject.

The investigator must document the nature of and reasons for the unsuccessful implant on the Implant Form. Subjects who have an unsuccessful upgrade will not be eligible for re-implantation attempts of an atrial LP at a later date during the study period.

Clinical Investigation Plan for Europe

6.2.9 Subjects without any LPs implanted

Investigators will follow subjects who leave an attempted *de novo* implant procedure without any implanted Aveir LPs for a period of at least 30 days to evaluate for adverse events. At the end of the 30 days, the investigator will withdraw the subject.

The investigator must document the nature of and reasons for the unsuccessful implant on the Implant Form. Subjects who have an unsuccessful implant will not be eligible for re-implantation attempts of any Aveir LPs at a later date during the study period.

6.2.10 Healthcare Utilization

Procedural and post-procedural healthcare utilization information will primarily be used for health economics and reimbursement research purposes. All inpatient hospitalizations, outpatient services, emergency room and urgent care visits for cardiac or non-cardiac reasons, including any associated with LP system revision procedure(s) should be reported to the Sponsor via a Healthcare Utilization Form. Any supporting documentation (i.e., Admission/Discharge Summary) that is available should also be submitted to the Sponsor via the EDC system.

Healthcare utilization data to be collected includes the type, a subject's final primary diagnosis, any procedures performed, and billing information (if applicable). Submission of a Healthcare Utilization Form for the index LP implant procedure itself, without associated adverse events, is optional.

6.2.11 Data Submission

Once the site has collected the required information and completed the required testing, the site will complete and submit the following case report forms to Abbott Medical using the EDC system:

- Implant Forms
- Aveir LP Assessment and Programming Form (Implant) with device session print out PDFs
- Device Accountability Log
- Healthcare Utilization Form, if applicable
- Adverse Event Form, if applicable
- Device Deficiency Form, if applicable
- Deviation Form, if applicable
- COVID-19 Assessment Log, if applicable
- Study Withdrawal Form, if applicable

Clinical Investigation Plan for Europe

All imaging data obtained for the purpose of right atrial characterization (e.g. ICE) should be de-identified and submitted to the Sponsor.

Any cinefluoroscopy imaging should be de-identified and submitted to the Sponsor upon Sponsor request.

6.3 System Revision with a Replacement Aveir LP

In the event an Aveir LP must be replaced during the follow-up period, investigators may opt to replace the first Aveir LP with a new Aveir LP in one of the following ways:

- Retrieve the first Aveir LP and implant a new Aveir LP
- Deactivate the first Aveir LP and implant a second Aveir LP in close proximity to the first

When considering Aveir LP retrieval and replacement, investigators will refer to the respective IFUs. Sponsor representatives may also assist the team in equipment setup prior to and during a procedure. If the subject receives a new Aveir LP, the subject must continue with his/her ongoing follow-up schedule.

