6.6 Follow-up Assessments

The site will perform the required clinical follow-up at the following intervals for all subjects implanted with an Aveir DR LP system:

- 1 month (\pm 15 days) follow-up site visit
- 3 month (\pm 30 days) follow-up site visit
- 6 month (\pm 30 days) follow up site visit
- 12 month (\pm 45 days) follow up site visit
- Every 6 months thereafter until study completion (\pm 45 days)

Please refer to Section 13.0 for more details on the conditions of study completion.

Dates for follow-up visits will be calculated from the date of the implant procedure. Follow-up assessments can be performed at any point within the pre-specified follow-up visit window.

Every effort should be made by the site personnel to have the subject return to the investigational site for all follow-up visits. If, despite all efforts, the subject is unable to return to the site during a follow-up window, subjects may undergo a remote follow-up assessment to collect applicable non-device performance data. Remote assessments should include telephone contact with the subject and/or a visit to a medical facility with all data that can be reasonably and legally collected remotely on the study subject. Follow-up visits occurring at non-study sites will be limited to standard of care data collection only. Authorization for the release of medical records from a non-study facility is the responsibility of the investigational site. Any missed testing will be considered a protocol deviation.

An enrolled subject may only be followed at another investigational site with prior agreement from that site's Investigator and from the Sponsor.

6.6.1 1-Month Follow-Up Visit

The 1-month follow-up visit will occur 30 days (\pm 15 days) post-implant procedure and will include the following assessments:

- Assess for adverse events and deviations from investigation plan
- Assess for changes in beta blockers, ACE, ARB, anti-coagulants, anti-platelets, anti-arrhythmics
- Assess Quality of Life (EQ-5D 5L)
- Measure and record LP performance, as described in Section 6.2.5 LP Assessment and Programming
- Program Aveir LP and adjust programmable parameters of LP, as needed

Clinical Investigation Plan for Europe

- **Optional:** 6-Minute Walk Test (6MWT) only for those capable *de novo* subjects who may be appropriately programmed temporarily in AAIR mode and who have a tolerance of high sensor-driven rates²

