6.6.3.1 Data submission

The site will complete and submit the following case report forms and device print outs to Abbott Medical using the EDC system:

- Follow-up Visit Form (includes medication changes)
- Aveir LP Assessment and Programming Form (Follow-Up) with device session print out PDFs
- Quality of Life Assessment (EQ-5D 5L)
- CAEP Exercise Test Form, if applicable
- Adverse Event Form, if applicable
- Device Deficiency Form, if applicable
- Deviation Form, if applicable
- Device Accountability Log, if applicable

Clinical Investigation Plan for Europe

- System Revision Form, if applicable
- Healthcare Utilization Form, if applicable
- COVID-19 Assessment Log, if applicable
- Study Withdrawal Form, if applicable

All source documentation associated with the CAEP, including device session printouts, source worksheets, and LP data files should be de-identified and submitted to the Sponsor.

6.6.4 12-Month Follow-Up Visit and Each Follow-up Visit Every Subsequent 6 Months until Study Completion

The 12-month follow-up visit will occur 365 days (± 45 days) and subsequently every 180 days (± 45 days) post-implant procedure and will include the following assessments:

- Assess for adverse events and deviations from investigation plan
- Assess for changes in beta blockers, ACE, ARB, anti-coagulants, anti-platelets, anti-arrhythmics
- Assess Quality of Life (EQ-5D 5L) - 12 month visit only
- Measure and record LP performance, as described in Section 6.2.5 LP Assessment and Programming
- Program Aveir LP and adjust programmable parameters of LP, as needed

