8.2.2 Primary Effectiveness Endpoint #1 Analyses

The primary effectiveness endpoint #1 evaluates the 12-month composite success rate (Rate_{EP}) of acceptable atrial pacing thresholds and P-wave amplitudes in *de novo* subjects.

Parameter	Acceptable values
Pacing voltage	Pacing threshold ≤ 3.0 V at 0.4 ms
P-wave sensitivity	P-wave amplitude ≥ 1.0 mV

The primary effectiveness endpoint #1 hypothesis is:

$$H_0: \text{Rate}_{EP} \leq 80\% \quad \text{vs.} \quad H_1: \text{Rate}_{EP} > 80\%$$

where 80% is the PG

The Rate_{EP} is the proportion of subjects who have met success criteria in the primary effectiveness endpoint #1.

Success Criteria: A subject will meet the primary effectiveness endpoint #1 endpoint if: pacing threshold voltage ≤ 3.0 V at 0.4 ms at the 12-month visit **and** the sensed P-wave amplitude is ≥ 1.0 mV at the 12-month visit.

The Rate_{EP} will be estimated as a binomial proportion and the 97.5% LCB of the Rate_{EP} will be calculated using the normal approximation. The null hypothesis is rejected at the 2.5%

Clinical Investigation Plan for Europe

significance level if the LCB exceeds the PG of 80%. The p-value for the one-sided Z-test will be calculated and compared to the 2.5% significance level.

The Sponsor will analyze the primary effectiveness endpoint #1 on both the full analysis (primary analysis) and implanted populations. In the full analysis population, subjects with unsuccessful implants due to reasons other than atrial pacing/sensing (e.g. cardiac anatomy) will be excluded from the analysis. Subjects who don't meet pacing/sensing success criteria at 12 months or subjects with unsuccessful implant solely due to unacceptable atrial LP pacing or sensing will be counted as failures. Additionally, for subjects with missing 12-month pacing threshold or P-wave amplitude data, a multiple imputation analysis will be used to impute the missing outcomes.

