The primary analysis for the primary effectiveness endpoint #1 will be based on subjects in the full analysis population. Subjects with unsuccessful implants due to reasons other than atrial pacing/sensing (e.g. cardiac anatomy) will be excluded from the analysis. Subjects who don't meet pacing/sensing success criteria at 12-months or subjects with unsuccessful implant solely due to inadequate atrial LP pacing or sensing will be counted as failures. Additionally, subjects with missing 12-month pacing threshold or P-wave amplitude data, multiple imputation will be used to impute success or failure.

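### Primary effectiveness endpoint #1 has no readable rule that counts an atrial LP replaced or removed after implant as a failure, so a post-implant device failure can be scored as a success or imputed

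*Protocol*

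**What the plan says.** **Replacement.** CIP 6.3 provides: "In the event an Aveir LP must be replaced during the follow-up period, investigators may opt to replace the first Aveir LP", either by retrieving it or by deactivating it and placing another close by. It continues: "If the subject receives a new Aveir LP, the subject must continue with his/her ongoing follow-up schedule". CIP 6.6 adds: "Dates for follow-up visits will be calculated from the date of the implant procedure". No restart at revision is stated.

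**Removal without replacement.** Under CIP 6.4, a subject who still has at least one active Aveir LP after a revision stays on the schedule. A subject with none is followed for at least 30 days and then withdrawn.

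**Scoring.** CIP 8.2.2 states: "A subject will meet the primary effectiveness endpoint #1 endpoint if: pacing threshold voltage ≤ 3.0 V at 0.4 ms at the 12-month visit", together with a P-wave of at least 1.0 mV at the same visit. SAP 2.3.2 has the same criteria. Neither ties the measurement to the LP first implanted.

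**Failures.** There are two kinds: criteria not met at 12 months, and, in the SAP's words, "subjects with unsuccessful implant solely due to inadequate atrial LP pacing or sensing will be counted as failures". CIP 8.2.2 has nearly the same sentence. CIP Appendix II judges an unsuccessful implant on the subject's state when leaving the implant procedure.

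**Missing data.** Missing 12-month values are multiply imputed. The readable sensitivity analyses for this endpoint in SAP 2.8 (complete case and tipping point) deal with missing data.

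**The concern.** Endpoint #1 is the trial's test of whether the atrial LP paces and senses as intended (CIP 4.1.2.1), and one of three endpoints supporting the AAI(R) indication (CIP 1.1.2). An atrial LP that loses capture or sensing after implant and has to be replaced has failed at that task. If only the replacement's value is read, the failure leaves no trace in the rate. The value may also come from a device implanted well under 12 months earlier, because the calendar is not reset.

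Compared with counting such subjects as failures, the present scoring can only raise the rate. In a single-arm comparison with a fixed goal, no control arm shares that shift. Imputation and the readable sensitivity analyses do not reach a replaced subject, because nothing is missing.

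**Working it through.** **1. Scoring path, step by step**

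| Event after the index procedure | What the readable text does | Endpoint #1 result |
|---|---|---|
| Atrial LP replaced by a new Aveir LP (CIP 6.3) | Same calendar; LP performance measured at 12 months (CIP 6.6.4) | Success if the replacement meets the criteria |
| Atrial LP retrieved or deactivated, not replaced, ventricular LP active (CIP 6.4) | Follow-up continues; no atrial values | Missing, multiply imputed |

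The second row takes imputation as the natural reading. SAP 2.3.2 also excludes subjects whose two values are both unobtainable because of rhythm conditions or procedures. If that were read to cover a removed LP, the subject would be excluded, which is still not a failure.

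**2. Pass mark**

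Inputs: 240 evaluable subjects (CIP 8.3, SAP 2.4); goal 80%, one-sided 2.5%, normal-approximation lower bound (CIP 8.2.2, SAP 2.3.2). The assumed rate and power behind the 240 are redacted, so that figure cannot be reproduced.

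Bound = p − 1.96 × √(p(1 − p)/240); pass if it exceeds 0.80.

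- 203/240 = 84.58%: 0.8458 − 1.96 × 0.0233 = 80.01%, pass.
- 202/240 = 84.17%: bound 79.55%, fail.
- 200/240 = 83.33%: 0.8333 − 1.96 × 0.0241 = 78.6%, fail.

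The mark is 203. Both documents also mention a Z-test. If it used the null variance the mark would be 205, which does not change the argument.

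**3. How many recoded subjects change the result**

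Each replaced subject moved from success to failure costs 1/240 = 0.42 points. With x scored successes, the result flips once x − 202 subjects are recoded.

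| Scored successes | Bound | Recoded subjects needed to flip | Example |
|---|---|---|---|
| 203 | 80.01% | 1 | 3 recoded: 200, bound 78.6%, fail |
| 206 | 81.4% | 4 | 5 recoded: 201, bound 79.1%, fail |
| 211 | 83.8% | 9 | 12 recoded: 199, bound 78.2%, fail |
| 228 | 92.2% | 26 | 12 recoded: 216, bound 86.2%, pass |

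**4. Chance of passing, under assumed replacement rates**

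Suppose the true rate with replaced subjects counted as failures is exactly 80%. The chance of passing is the exact binomial P(X ≥ 203) with n = 240 and success probability 0.80 plus the share replaced and scored as successes.

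| Share replaced and scored as success (assumed) | Chance of passing |
|---|---|
| 0% | 4.2% |
| 1% | 8.9% |
| 2% | 16.9% |
| 3% | 29.0% |

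The 4.2% already exceeds 2.5% because of the normal approximation; only the rise above it belongs to this point.

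The cost in power of the stricter rule depends on the true scored rate. Recoding 2% of subjects lowers power from 95.4% to 76.9% at a scored rate of 88%, and from 99.7% to 95.4% at 90%. At 95% it makes no practical difference.

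**The case against.** **Scoring the final device state is a choice.** The endpoint is a point measurement at the 12-month visit. Taking the subject's value regardless of revision is a legitimate treatment-policy approach, and CIP 4.1.2.1 says these measurements are stable from as early as 2 weeks. This stands in part: a younger replacement LP is not necessarily a misleading reading. But stability of the values does not explain why the failed first device should drop out, and the plan neither states nor justifies such a choice.

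**Device failures belong to safety.** An event needing an invasive remedy meets the serious-event definition in CIP Appendix II. A revision is therefore likely to count in the primary safety endpoint (goal 76.5%) and, if atrial, in the secondary safety endpoint (goal 82%), subject to adjudication. The AAI(R) claim rests on several endpoints together. This also stands, so the failure is probably not lost to the trial. It does not correct the rate tested against 80%.

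**A reader might infer an inconsistency with the index procedure**, namely that the same fault at implant is always a failure. The documents do not support that. CIP 6.2.6 allows a released LP to be removed and another Aveir LP tried, and Appendix II looks only at the state on leaving. A poor LP exchanged for a good one during the index procedure is therefore a successful implant. Only a subject who leaves with an unsuccessful implant solely because of atrial pacing or sensing is failed.

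**A reader might also infer that the plan declares these subjects successes.** No sentence does; the result follows from rules that do not mention revision. Text is redacted after the full-analysis definition and in SAP 2.7, 2.8 and 7.0, and a rule could be there. If so, a cross-reference from SAP 2.3.2 would settle the matter.

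**Conclusion.** The point holds as a gap in the readable scoring rule. An atrial LP that failed after implant and was replaced can count as an endpoint #1 success; one taken out of service without replacement is imputed, not failed. Measured against a rule that counts these as failures, the shift goes one way, towards passing.

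Its size is unknown because the documents give no revision rate. It can decide the test only when the observed rate is near 203/240 (84.6%). The chance-of-passing figures assume a true rate exactly at the goal and a chosen share of replaced subjects scored as successes. They show sensitivity to the rule and are not evidence that the trial's error rate is inflated by those amounts. The plan should settle the rule before the 12-month data are seen, because a few subjects could decide a close result.

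**What to change.** Add to SAP 2.3.2 and CIP 8.2.2 a scoring rule such as:

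> *A subject whose atrial LP was replaced, repositioned, retrieved or deactivated after the index procedure and before the 12-month measurement because of inadequate atrial capture or sensing, including from dislodgement, is an endpoint #1 failure and is not imputed.*

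Report the result using replacement-LP values as supplementary. Retrieval and deactivation must be covered as well as replacement; otherwise a subject with a working replacement would be failed while one with no atrial LP could be imputed as a success.

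At minimum, keep the present scoring, say so explicitly, and pre-specify this failure count as a sensitivity analysis in SAP 2.8.

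Take the reason for revision from the System Revision Form, which CIP 6.3.1 and 6.4.1 already require. The cost is wording only, and clinical management is untouched. The downside is that the reported success rate may be slightly lower, with some loss of power if the true rate is close to the goal.
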